### 6.2.5. Vector Shedding

The peak value, time to peak value, and time to undetectable/negative vector (first of 3 consecutive negative results), time to last of 3 consecutive negative results, and time to last positive result prior to 3 consecutive negative results will be summarized by specimen type, stratified by dose level. Number and percentage of participants who achieved 3 consecutive negative results will be reported for each specimen. Peak value information and time to undetectable/negative vector will also be presented in a data listing. Vector genome values for each study visit will be listed by specimen type. Individual profile plots of vector genome values over time (log scale) will be presented by dose level for each specimen type.

## 6.3. Exploratory Endpoints

All summaries and listings of exploratory endpoints will be based on the Safety population.

### **6.3.1. FVIII Antigen**

FVIII antigen levels will be summarized by visit and dose level and presented in a data listing.

### **6.3.2. Immunogenicity**

The results of the following parameters will be presented in a data listing. Individual profile plots of the values over time will be presented by dose level, if appropriate.

- Total and neutralizing antibodies to AAV2/6;
- Cellular responses against FVIII and AAV2/6 (ELISPOT assay);
- Measurements of CRP and IL6.

### **6.3.3. Von Willebrand Factor**

Von Willebrand Factor will be summarized for observed values and change from baseline by visit and dose level and presented in a data listing.

### **6.3.4. GAL3BP and sEGFR**

Baseline values for sEGFR and Gal3BP will be presented in a data listing.

### **6.3.5. FVIII Steady State**

Mean and median values of FVIII levels using chromogenic and one-stage assays will be presented as a box and whisker plot by visit for Cohort 4 ( $3 \times 10^{13}$  vg/kg) to assist in determining the onset of steady state of transgene expression.

### **6.3.6. Optional Liver Biopsy Substudy**

Liver biopsy will be performed on few participants only and most probably at different timepoints for each participant, so mainly a description of the findings for each biopsy will be provided.

## **6.4. Subset Analyses**

Not applicable.

## **6.5. Baseline and Other Summaries and Analyses**

### **6.5.1. Baseline Summaries**

All baseline characteristics will be summarized by dose level and overall for the Safety population. The following parameters will be summarized:

- Age (in years) at informed consent (IC), calculated as the integer part of (Date of IC – Date of Birth)/365.25; if only year of birth is collected, then age will be calculated as (Year of IC – Year of Birth);
- Race;

---

- Ethnicity;
- Sex;
- Weight (kg) at screening and baseline;
- Height (cm) at screening;
- BMI (kg/meter [m]) at screening (calculated as [(weight in kg)/(height in cm)]\*10000);
- 12-lead ECG at screening, n (%) of normal result.

Listings of baseline characteristics will also be created.

### **6.5.2. Study Conduct and Participant Disposition**

The number of screened participants will be summarized. For screen failures, the reason for screen failure will be summarized using counts and percentages. No stratification by dose level will be implemented for this analysis. Enrolled participants are those who have been screened, are not considered to be a screen failure, and who have been approved by the Medical Monitor. A participant will be considered to have completed the study if he has completed all phases of the study including the End-of-Study visit (Month 60).

The number of participants enrolled, completing the study, discontinuing from the study and the primary reason for discontinuation, and the number of deaths (if any), will be summarized (number and percentage of enrolled participants in each population used for analysis), stratifying by dose level and overall. The number of ongoing participants will be included for outputs provided prior to the final analysis.

Listings will be provided for participant disposition, along with reasons for exclusion or discontinuation. An additional participant-level listing will be provided, indicating each observation period (Year) that he entered, and his duration in that period, along with his total study duration, as of the date of data cut (or conclusion date).

Potentially important protocol deviations (corresponding to those reported as 'Major') will be presented in a data listing.

### **6.5.3. Study Treatment Exposure**

The total amount of IP taken by participant (vg) will be summarized for the Safety population by dose level. The number and percent of participants receiving the intended dose and experiencing interruptions during dosing will also be summarized. The doses corresponding to the 4 cohorts are: 9x10^11vg/kg (cohort 1), 2x10^12vg/kg (cohort 2), 1x10^13vg/kg (cohort 3), and 3x10^13vg/kg (cohort 4).

A listing of IP administration will be created.

#### 6.5.4. Concomitant Medications and Nondrug Treatments

During the first 3 years, all concomitant medications are to be recorded on the participant's eCRF, as well as any AEs related to administration of these medications.

During Years 4 and 5 post-IP infusion, only concomitant medications associated with SAEs or AEs assessed as related to investigational product by the investigator or where causality is unknown are to be recorded.

All concomitant procedures will be recorded in the eCRF throughout the entire duration of the study.

Medications will be coded with World Health Organization Drug Dictionary (WHO DD) using the most recent version in place at the time of data cut or data base release, providing Anatomical Therapeutic Chemical (ATC) level 2 and ATC level 4 codes for each medication. A medication will be considered prior if its end date is before the IP infusion, and concomitant otherwise. The number and percentage of participants taking prior and concomitant medications will be summarized by ATC codes for the Safety population. All summaries will be presented by dose level and overall. Prior FVIII replacement therapy will be defined and summarized similarly to prior medications. In a similar manner, concomitant procedures will be summarized by SOC and PT.

Prior and concomitant medications, post-IP infusion FVIII replacement therapy, previous FVIII replacement therapy, and concomitant procedures will be presented in separate listings.

To assess corticosteroid treatment after PF-07055480 infusion, the following data will be summarized and presented in a listing for Cohort 4 ( $3 \times 10^{13}$  vg/kg):

- Duration of corticosteroid courses. All consecutive corticosteroid treatment records with  $\leq 3$  days between the last day of the prior record and the first day of the following record will be considered one course.
- Total duration of corticosteroid treatment per participant, defined as the sum of the duration of all courses for each participant.

Individual profile plots containing liver function data, FVIII activity, and corticosteroid use over time will be presented for Cohort 4 ( $3 \times 10^{13}$  vg/kg).

Additionally, a listing of the participants who took steroids during the study in the Safety population will be provided.

#### 6.5.5. Hemophilia History, Medical History and Concurrent Medical Conditions

Medical history will be summarized with counts and percentages of participants by SOC and PT for each dose level and overall for the Safety population.

Concurrent and prior conditions will be listed. A condition will be considered prior if its end date is before the IP infusion, and concurrent if its end date is after the IP infusion. In case of

missing end date, a condition will be considered concurrent if it was ongoing at screening, and prior otherwise.

Hemophilia history data will be summarized by dose level and overall for the Safety population. The following parameters will be included in the summary: time since hemophilia diagnosis (calculated as (date of IC - date of diagnosis)/365.25), hemophilia severity grade at screening, type of FVIII treatment, history of FVIII inhibitors, number of bleeding episodes in the last 12 months (overall and by severity), time since last BE (in days; calculated as date of IC - date of last BE), number of participants with target joints, and target joint/body area. A disease history listing will also be created.

At the Screening visit, the FVIII Regimen History eCRF is used to collect, “all prior FVIII treatments the subject took, starting 12 months prior to screening and ending 30 days prior to screening”. This infusion data will be summarized separately as part of Prior and Concomitant Medications.

## 6.6. Safety Summaries and Analyses

All safety analyses, including analyses of AEs, clinical laboratory results, vital signs, ECG, and physical examinations will be conducted on the Safety analysis population.

### 6.6.1. Adverse Events

All AEs will be summarized for the Safety population, by dose level and overall across dose groups. AEs by Year 1, 2, 3, 4, and 5 will be presented.

Both all-causality AEs and treatment-related AEs will have similar summaries presented descriptively. All data will be included in the summary as appropriate, with clarifying footnotes describing the types of AEs collected in each reporting period.

The number and percentage of participants with any TEAE, any treatment-emergent SAE, any treatment-related TEAE, any serious treatment-related TEAE, and any TEAE leading to discontinuation from the study will be presented for all participants by dose level and overall.

All TEAEs, treatment-emergent SAEs, and treatment-related TEAEs will be summarized by SOC and PT; all TEAEs and treatment-related TEAEs will also be summarized by SOC, PT and Common Terminology Criteria for Adverse Events (CTCAE; version 4.03) severity grade. Summaries will include the number and percentage of participants in each SOC, PT, or CTCAE severity grade by dose level and overall. Adverse events of special interest (AESI) will be identified in summaries by SOC and PT.

Separate listings of TEAEs, SAEs, TEAEs leading to discontinuation from the study, and AEs leading to death (if any) will be produced. A listing of deaths will be provided as well, including the date and information about the primary reason for death.

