8.3.1. Time Period and Frequency for Collecting AE and SAE Information

The time period for actively eliciting and collecting AEs and SAEs (“active collection period”) for each participant begins from the time the participant provides informed consent, which is obtained before the participant’s participation in the study (ie, before undergoing any study-related procedure and/or receiving study intervention), through and including to the last visit (completion at 60 months [± 1 months]) or at ETV for participants who discontinue.

However, from Month 36 through to the end of study (Month 60), only the following AEs will be actively collected:

- SAEs
- Non-serious AEs determined to be related to study intervention by the investigator or where causality is unknown.

Follow-up by the investigator continues throughout and after the active collection period and until the AE or SAE or its sequelae resolve or stabilize at a level acceptable to the investigator and Pfizer concurs with that assessment.

For participants who are screen failures, the active collection period ends when screen failure status is determined.

If the participant withdraws from the study and also withdraws consent for the collection of future information, the active collection period ends when consent is withdrawn.

If a participant definitively discontinues or temporarily discontinues study intervention because of an AE or SAE, the AE or SAE must be recorded on the CRF and the SAE reported using the CT SAE Report Form.

Investigators are not obligated to actively seek AEs or SAEs after the participant has concluded study participation. However, if the investigator learns of any SAE, including a death, at any time after a participant has been discharged from the study, and he/she considers the event to be reasonably related to the study intervention or study participation, the investigator must promptly notify the sponsor.

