#### 3.1. Primary Endpoints

##### 3.1.1. Incidence of Adverse Events and Serious Adverse Events

For Years 1 to 3, all serious and non-serious AEs will be collected. For Years 4 and 5, all SAEs (regardless of relation to study intervention) and non-serious AEs determined to be related to study intervention by the investigator or where causality is unknown will be collected.

Incidence of AEs and SAEs, include clinically significant changes from pre vector dosing in:

- physical examinations;
- clinical laboratory assessments;
- immune parameters;
- vital signs;
- ECG;
- liver imaging.

Abnormal findings that meet the criteria for AE reporting in this study are to be reported as AEs, and thus will be included in the primary endpoint summary table.

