## **6. ANALYSES AND SUMMARIES**

### **6.1. Primary Endpoints**

#### **6.1.1. Incidence of Adverse Events and Serious Adverse Events**

During Years 1, 2, and 3 all AEs are to be collected, and during Years 4 and 5, treatment-related AEs (plus all-causality SAEs) are to be collected.

Incidence of adverse events will be presented descriptively. In addition, incidence of treatment-related adverse events will be similarly presented. Summaries will be presented by dose level and overall. AE tables by year will show columns for each dose level and overall, and separate pages for each of the five yearly periods as described in [Section 5.2](#) (Year 1, 2, 3, 4, and 5), with denominator (number of participants still being followed at the beginning of each year) and counts (%) of participants in each, corresponding to the onset date of AE.

The incidence and severity of AEs will be tabulated and grouped by system organ class (SOC) and preferred term (PT). In addition, all serious AEs (regardless of causality) will be summarized separately. A summary table including severity graded by CTCAE version 4.03, for those events that are possible to rate, will also be provided.

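### All-causality AE tables for Years 4-5 and for the entire study cross the Month 36 cut in AE collection; the footnote discloses the under-count but no like-for-like table replaces it

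*SAP*

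**What the plan says.** Protocol 8.3.1 narrows AE collection part-way through follow-up: "However, from Month 36 through to the end of study (Month 60), only the following AEs will be actively collected". The list that follows has two items, SAEs and "Non-serious AEs determined to be related to study intervention by the investigator or where causality is unknown". The recording table in Protocol 10.3.3 has the same cut at Month 36.

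The SAP knows of the change. Section 3.1.1 states "For Years 1 to 3, all serious and non-serious AEs will be collected", and describes Years 4 and 5 as the protocol does. Section 6.1.1 says that "during Years 4 and 5, treatment-related AEs (plus all-causality SAEs) are to be collected", leaving out the unknown-causality category that Protocol 8.3.1 and SAP 3.1.1 both include.

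The planned output does not narrow with the collection. In SAP 6.1.1, "AE tables by year will show columns for each dose level and overall", with "separate pages for each of the five yearly periods as described in" SAP 5.2. The denominator is the number still followed at the start of each year. SAP 6.6.1 repeats that "AEs by Year 1, 2, 3, 4, and 5 will be presented" and gives all-causality and treatment-related AEs similar summaries, "with clarifying footnotes describing the types of AEs collected in each reporting period". SAP 3.5.1 adds AE reporting across the entire study. All-causality SAEs are summarised separately in 6.1.1 and 6.6.1, without an explicit statement that this is done by year.

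**The concern.** AE incidence is a primary endpoint, and Protocol 9.4.3 says participants are followed through Years 2 to 5 for further data on safety and durability. A reader given five yearly pages of the same all-causality table will read them as a series. The last two pages rest on a narrower event definition: a non-serious AE judged unrelated counts in Year 3 and is not actively sought in Year 4.

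Two outputs are affected. The Year 4 and Year 5 all-causality pages carry a label that their content does not meet. The entire-study all-causality tables (any TEAE, by SOC and PT, by CTCAE grade) combine three years of full capture with two years of partial capture, so they estimate the incidence of no single event class over five years. The grade distribution can also shift, because SAEs stay in while unrelated non-serious events drop out.

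**Working it through.** The documents state no AE rate, so there is no figure of the plan's own to reproduce. The check sets the collection rule beside the tables, then illustrates the direction of the effect with assumed rates.

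**Collection against tabulation**

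| Event class | Collected Years 1-3 | Actively collected Years 4-5 | Planned summary |
|---|---|---|---|
| SAE, any causality | yes | yes | separate summary, not explicitly by year |
| Non-serious, related | yes | yes | treatment-related tables, by year |
| Non-serious, causality unknown | yes | yes (omitted in SAP 6.1.1) | all-causality; in the treatment-related tables only if counted as related |
| Non-serious, unrelated | yes | no | all-causality, Years 1-5 and entire study |

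The last row is the mismatch. No planned table is restricted to the first three rows together. The number of participants with at least one event in those rows cannot be obtained by adding SAE and treatment-related counts, because one participant may appear in both.

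**Illustration of the yearly step.** Assumptions, none from the documents: Poisson events, a constant true rate *r* per participant-year, and a share *s* of AEs that are non-serious and unrelated. The share of participants with at least one collected AE in a year is

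- Years 1-3: 1 − exp(−*r*)
- Years 4-5: 1 − exp(−*r*(1 − *s*))

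| *r* | Years 1-3 | Years 4-5, *s* = 0.25 | *s* = 0.50 | *s* = 0.75 | *s* = 0.90 |
|---|---|---|---|---|---|
| 0.5 | 39.3% | 31.3% | 22.1% | 11.8% | 4.9% |
| 1 | 63.2% | 52.8% | 39.3% | 22.1% | 9.5% |
| 2 | 86.5% | 77.7% | 63.2% | 39.3% | 18.1% |
| 4 | 98.2% | 95.0% | 86.5% | 63.2% | 33.0% |

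The direction is the same in every cell; the size runs from 3 to 68 percentage points. To keep the collected event rate level across Month 36, the classes still collected would have to rise by 1/(1 − *s*), that is by a factor of 1.33, 2, 4 or 10.

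**Entire study.** Under the same assumptions the five-year share with any AE is 1 − exp(−5*r*) with full capture and 1 − exp(−(3*r* + 2*r*(1 − *s*))) as planned. For *r* = 0.5 and *s* = 0.75 this is 1 − exp(−2.5) = 91.8% against 1 − exp(−1.75) = 82.6%. For *r* = 1 and *s* = 0.75 it is 99.3% against 97.0%. The overall any-AE row may therefore change little when AEs are frequent; the gap is wider at the lower rate.

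**After restriction.** If every year is limited to the classes collected throughout, the figure is 1 − exp(−*r*(1 − *s*)) in all five years, and the artificial step is zero.

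**Year 3/Year 4 boundary.** Month 36 is 36 × 365.25/12 = 1095.75 days. SAP 5.2.1.1 ends Year 3 at Day 1095, so the window and the rule agree to within about a day. If sites switched at the Month 36 visit (±1 month), the change could fall between 35 × 30.4375 = 1065 and 37 × 30.4375 = 1126 days, but the documents tie the rule to Month 36 and not to a visit date.

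**The case against.** The best defence is that the SAP already handles most of this. It states the collection change twice, gives each year its own page and denominator, plans treatment-related tables in the same form, summarises all-causality SAEs separately, and footnotes what was collected when. Protocol 10.3.3 treats an event of unknown causality as related for reporting purposes; if tabulation follows that rule, the treatment-related tables and the SAE summary between them cover every class collected for five years. With about 20 participants and full listings, a reader could assemble the rest. The analyses are descriptive and no contrast between years is planned.

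Much of that stands. A reader might infer that the footnote is the only safeguard in the SAP; it is not. It is the only stated remedy within the all-causality tables. A reader might also infer that AE incidence must fall in Years 4-5. The documents do not support that: reduced capture means the figure cannot exceed what full capture would give, but whether it falls from Year 3 depends on AE rates they do not report. Nor is there a case for moving the Year 3/Year 4 boundary to a date specific to each participant. Day 1095 already matches nominal Month 36, and no such date is defined.

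The defence does not supply a by-year count of participants with any event in the classes collected throughout, or an entire-study figure with a single meaning. The SAP does not say that unknown causality counts as related in its tables. SAP 3.5.1 applies the yearly windows to AE reporting in general, so SAEs by year may be intended, but this is not explicit.

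**Conclusion.** The point holds as a reporting weakness in a primary-endpoint summary. All-causality AE figures for Years 4-5 are biased downward relative to Years 1-3, and the entire-study all-causality figures pool two collection regimes. Both follow directly from the collection rule and the table plan. Disclosure by footnote does not make the numbers comparable.

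The size is unknown. The percentages above depend on assumed rates, an assumed unrelated share and a constant Poisson rate; they show direction only and predict nothing about this trial. The treatment-related tables are comparable across years, provided unknown-causality events are handled the same way throughout. No hypothesis test or decision rule depends on the affected tables. It is worth correcting because one filter on data already collected gives a series that can be read across years.

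**What to change.** In SAP 6.1.1 and 6.6.1:

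- **(a)** Present the full all-causality TEAE summaries by year for Years 1-3 and cumulatively through Month 36. Title any Year 4-5 or entire-study version for its content: SAEs plus related or unknown-causality non-serious AEs.
- **(b)** Add one table for Years 1-5 and the entire study, restricted in every year to SAEs plus non-serious AEs that are related or of unknown causality. State that the SAE summary is also given by year. Bring the SAP 6.1.1 description of Years 4-5 into line with SAP 3.1.1 and Protocol 8.3.1 by adding unknown causality.

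Keep the Day 1095 boundary and the planned footnotes.

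The cost is SAP wording, some retitling and one extra filtered table; no new data are needed. The downside is that unrelated non-serious AEs captured incidentally after Month 36 would appear only in listings.

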### 6.6.2. Laboratory Data

All samples will be analyzed by a central laboratory (liver panels may also be done locally in certain circumstances, only listings will be provided for local liver panel data). Likewise,

although FVIII activity assessments are to be analyzed by both local and central laboratories, only central laboratory values will be summarized, and local laboratory values will be reported in a listing. No local laboratory data will be summarized in this study.

Descriptive statistics of actual values and change from baseline for all liver function tests (LFT) will be presented by time point. Summaries will be performed based on the Safety population, by dose level and overall. All LFTs will also be presented in listings. Individual profile plots of the liver test values over time will be presented for each participant by LFT.

Safety laboratory tests and other laboratory tests specified in [Section 3.5.2](#) will be summarized.

Laboratory values outside of a laboratory's normal ranges will be flagged as H (high, above normal) or L (low, below normal) in laboratory data listings.

Tabulations for low, normal, and high test results will be presented by visit for selected parameters. A shift table of minimum and maximum on-study records will be created by baseline classification.

